### ***Change from baseline in fluctuation in 7-9-7-point profile***

The fluctuation in the 7-9-7-point profile is defined as:

$$\frac{1}{T} \int_0^T |PG(t) - \bar{PG}| dt$$

where T, PG(t) and  $\bar{PG}$  denotes the length of the profile, the PG value at time t and the mean of the profile, respectively.

*Fluctuation in the 7-9-7-point profile will be logarithmically transformed and analysed in the same way as mean of the profile is analysed except with the corresponding log-transformed baseline values as covariate.*

*Estimated treatment means and the estimated treatment difference with corresponding 95% CI will be back-transformed to the original scale, resulting in estimated geometric means, a treatment ratio and a 95% CI for the treatment ratio.*

~~Fluctuation in the 7-9-7-point profile will be logarithmically transformed and analysed in the same way as mean of the profile is analysed with log transformed baseline values.~~

### ***Change in the nocturnal SMPG measurements***

*Change from baseline in change in nocturnal PG values 26 weeks after randomisation will be assessed by considering the differences between PG values available at bedtime, at 4 AM and the before breakfast value the following day: (4 AM PG value minus at bedtime PG value), (before breakfast PG value minus at bedtime PG value) and (before breakfast PG value minus 4 AM PG value).*

*Change in the nocturnal SMPG measurements will be analysed in the same way as mean of the profile is analysed, except with the corresponding baseline values as covariate.*

**PPG responders (overall mean of daily PPG measurements in SMPG) after 26 weeks of treatment after randomisation:**

**Overall PPG (1 hour)  $\leq 7.8$  mmol/L [140 mg/dL]**

A dichotomous endpoint will be defined based on whether a subject has reached an overall mean 1 hour PPG  $\leq 7.8$  mmol/L [140 mg/dL] after 26 weeks of treatment after randomisation, where PPG is derived from the 7- and 9-point profile.

This responder endpoint will be analysed based on a logistic regression model using treatment, region and *bolus adjusting method* as factors, and baseline overall mean 1 hour PPG as covariate. *In analysis of the in-trial data subjects without an overall mean 1 hour PPG at week 26 will be treated as non-responders. In the on-treatment observation period analysis both subjects who discontinue faster-acting insulin aspart/NovoRapid® or withdraw from trial is included as non-responders. Predicted values from the MMRM model for overall mean 1 hour PPG will be used for all subjects with no PPG at the last visit.*

**Overall PPG (1 hour)  $\leq 7.8$  mmol/L [140 mg/dL] without severe hypoglycaemia**

A dichotomous endpoint will be defined based on whether a subject has reached an overall mean 1 hour PPG  $\leq 7.8$  mmol/L [140 mg/dL] after 26 weeks of treatment after randomisation without any treatment emergent severe hypoglycaemic episodes.

~~The withdrawals from their randomised treatment will be set to non-responders. This is based on the assumption that the subjects would experience a severe hypoglycaemia after the withdrawal. A predicted value from the MMRM model will be used if a treatment completer does not have overall mean 1 hour PPG at the last visit.~~

This responder endpoint will be analysed based on a logistic regression model using treatment, region and *bolus adjusting method* as factors, and baseline overall mean 1 hour PPG as covariate. *In analysis of the in-trial data subjects without an overall mean 1 hour PPG at week 26 will be treated as non-responders. In the on-treatment observation period analysis both subjects who discontinue faster-acting insulin aspart/NovoRapid® or withdraw from trial is included as non-responders.*

**Overall PPG (1 hour)  $\leq 7.8$  mmol/L [140 mg/dL] and HbA1c  $< 7.0\%$  and minimal weight gain ( $<3.0\%$ ) without severe hypoglycaemia**

A dichotomous endpoint will be defined based on whether a subject has reached an overall mean 1 hour PPG  $\leq 7.8$  mmol/L [140 mg/dL], have HbA1c  $< 7.0\%$  and has had minimal weight gain (increase in body weight from baseline  $<3.0\%$ ) after 26 weeks of treatment after randomisation, and without any treatment emergent severe hypoglycaemic episodes.

*This responder endpoint will be analysed based on a logistic regression model using treatment, region and bolus adjusting method as factors, and baseline overall mean 1 hour PPG, baseline HbA1c and baseline body weight as covariates. In analysis of the in-trial observation period subjects without an overall mean 1 hour PPG or an HbA1c value or a body weight at week 26 will be treated as non-responders. In the on-treatment observation period analysis both subjects who discontinue faster-acting insulin aspart/NovoRapid® or withdraw from trial is included as non-responders. The withdrawals from their randomised treatment will be set to non-responders. This is based on the assumption that the subjects would experience a severe hypoglycaemia after the withdrawal. A predicted value from the MMRM model will be used if a treatment completer does not have overall mean 1 hour PPG, HbA1c or body weight at the last visit.*

*This responder endpoint will be analysed based on a logistic regression model using treatment and region as factors, and baseline overall mean 1 hour PPG, baseline HbA1c and baseline body weight as covariates.*

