### **Classification of Hypoglycaemia:**

Treatment emergent: hypoglycaemic episodes will be defined as treatment emergent if the onset of the episode occurs on or after the first day of IMP administration after randomisation and no later than one day after the last day on IMP.

Nocturnal hypoglycaemic episodes: are episodes occurring between 00:01 and 05.59 both inclusive.

[figure not shown]
Hypoglycaemic episodes are classified according to the Novo Nordisk classification of hypoglycaemia (see [Figure 17-1](#) and the ADA classification of hypoglycaemia [Figure 17-2](#)).

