***eDiary records after premature discontinuation of trial product:***

*Date, actual clock time and value of the SMPG measurements performed as part of the 7-9-7-point profiles on the three consecutive days prior Visit 36A, Visit 22 and Visit 36*

*For hypoglycaemic episodes only the following information should be recorded from visit 36A and onwards:*

- *Start date and time of hypoglycaemic episode*
- *Value of plasma glucose level before treating the episode (if available) and any follow up measurements.*
- *Whether the episode was symptomatic (Yes/No)*
- *Whether the subject was able to treat him/herself*

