### General considerations

In general, for endpoints evaluated as a change from baseline and/or where a baseline adjustment is made, baseline is defined as information collected at the randomisation visit (Visit 10). In case a measurement is not available at the randomisation visit, the most recent measurement prior to the randomisation visit will be used as baseline.

*Two observation periods are defined, “in-trial” and “on-treatment”, and it will be specified which period each analysis will use.*

- *In-trial: the observation period from date of randomisation and until last trial-related subject-site contact. The in-trial observation period includes data collected after treatment discontinuation.*
- *On-treatment: the observation period from date of first dose of NovoRapid®/faster-acting insulin aspart and no later than 7 days after the day of last dose of NovoRapid®/faster-acting insulin aspart. The on-treatment observation period includes data collected up to and including 7 days after treatment discontinuation.*

*Analyses of efficacy endpoints will be based on the full analysis set (FAS). All efficacy endpoints will be summarised and analysed using the full analysis set (FAS), unless otherwise stated. Safety endpoints will be summarised using the safety analysis set (SAS) and analysed using the FAS.*

*Presentation of results from a statistical analysis will include the estimated mean treatment effects (LSMeans) for change from baseline, if applicable. Estimated mean treatment differences (or ratios) will be presented together with two-sided 95% confidence intervals for all endpoints analysed statistically.*

*For endpoints measured over time mean values will be plotted to explore the trajectory over time. For survival endpoints, e.g. drop-out pattern, Kaplan-Meier plots are presented for each treatment. Data collected before randomisation will only be summarised descriptively.*

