##### **2.29.4.1 Section 17.4.2.1 Efficacy endpoints**

*All endpoints except insulin dose in this section will be assessed using the FAS and the in-trial observation period and repeated using the on-treatment observation period. Insulin dose will be presented using SAS and will therefore only use the on-treatment observation period.*

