**HbA1c < 7.0% without severe hypoglycaemia and minimal weight gain (<3.0%)**

A dichotomous (responder/non-responder) endpoints will be defined based on whether a subject has met the ADA HbA1c target (HbA1c < 7.0%) ~~after 26 weeks of treatment after randomisation without treatment emergent severe hypoglycaemic episodes, and with minimal weight gain from baseline to 26 weeks of treatment after randomisation (defined as less than a 3% increase).~~

*This responder endpoint will be analysed based on a logistic regression model using treatment, region and *bolus adjusting method* as factors and baseline HbA1c and baseline body weight as covariates. In analysis of the in-trial data subjects without an HbA1c measurement at week 26 will be treated as non-responders. In the on-treatment observation period analysis both subjects who discontinue faster-acting insulin aspart/NovoRapid® or withdraw from trial is included as non-responders. The withdrawals from their randomised treatment will be set to non responders. This is*

~~based on the assumption that the subjects would experience a severe hypoglycaemia after the withdrawal. A predicted value from the MMRM model will be used if a treatment completer does not have HbA1c or body weight at the last visit.~~

~~This responder endpoint will be analysed based on a logistic regression model using treatment and region as factors and baseline HbA1c and baseline body weight as covariates.~~

**Change from baseline in 30- min, 1- hour, 2- hour, 3- hour and 4- hour PPG and in 30- min, 2- hour, 3- hour and 4- hour PPG increment ~~after 26 weeks of treatment~~ after randomisation (meal test)**

Laboratory measured PG from the meal test will be analysed for 30, 60, 120, 180, and 240 minutes PPG separately. The corresponding PPG increments will be derived separately using each PPG measurement minus the pre-prandial PG.

*Change from baseline in PPG and PPG increment endpoints 26 weeks after randomisation* ~~Change from baseline after 26 weeks of treatment in PPG and PPG increment endpoints~~ will be analysed separately using an ANOVA model including treatment, region and *bolus adjusting method* as factors, and the corresponding baseline value as covariate.

*Note as the meal test is only preformed once post baseline, subjects with no post baseline meal test will not contribute to the analysis.*

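### The in-trial responder endpoints that require no severe hypoglycaemia ignore severe episodes occurring after trial product is stopped

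*Protocol*

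**What the plan says.** Amendment 2, revised Section 17.4.2.1, states that all supportive efficacy endpoints except insulin dose "will be assessed using the FAS and the in-trial observation period and repeated using the on-treatment observation period". The revised general considerations in Section 17 are explicit about what the first of these periods covers: "The in-trial observation period includes data collected after treatment discontinuation".

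The simple PPG composite in the same section asks whether the overall mean 1-hour PPG is at or below 7.8 mmol/L at week 26 "without any treatment emergent severe hypoglycaemic episodes". The triple PPG composite uses the same phrase. The HbA1c composite with the weight condition reads "without treatment emergent severe hypoglycaemic episodes, and with minimal weight gain", and the HbA1c composite without it is worded alike.

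The window behind that term is in Section 17.4.2.2 of the base protocol, under the classification of hypoglycaemia. It ends "no later than one day after the last day on IMP", and Amendment 2 does not alter it.

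For subjects who stop product, the new Section 8.1.13 keeps the planned site visits to week 26, the 7-9-7-point profile before Visit 36 and the recording of hypoglycaemic episodes from Visit 36A onwards. One of the items still recorded is "Whether the subject was able to treat him/herself".

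**The concern.** A composite responder endpoint is one yes/no outcome, so its parts should refer to the same period. Here the glucose part runs to week 26 irrespective of treatment, while the hypoglycaemia part is switched off one day after product stops. A subject can therefore carry a recorded severe episode in the trial database and still be reported as having reached target without severe hypoglycaemia.

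At stake is what the in-trial responder rate means. It is not a treatment-policy rate, because severe episodes after discontinuation are left out. It is not an on-treatment rate, because glucose values after discontinuation are let in. The analysis is run for each of the two comparisons with mealtime NovoRapid®.

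**Working it through.** The plan gives no figure for this point, so there is none to reproduce. The check is a comparison of definitions, followed by a count of the subjects it can touch.

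**Step 1: the rules side by side (simple PPG composite)**

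| Element | In-trial analysis | On-treatment repeat |
|---|---|---|
| Glucose value | Week 26, on or off product | Week 26, on product |
| Severe hypoglycaemia | Treatment-emergent only: to last day on product + 1 day | Same |
| Who is a non-responder by rule | Only subjects with no week-26 value | Everyone who stops product or leaves the trial |

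In the right-hand column the short hypoglycaemia window does no harm, because anyone who stops product has already failed. In the middle column no rule closes the gap.

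**Step 2: can the case occur?** Take a subject who stops product at week 6, has a severe episode at week 15 and meets the target at week 26.
- Week-26 value available: yes, because Section 8.1.13 keeps Visit 36 and its SMPG profile.
- Episode recorded: yes, in the eDiary from Visit 36A onwards.
- Severity determinable: yes. Severe means needing another person's help, and ability to self-treat is recorded.
- Episode counted: no, because it falls well beyond one day after the last day on product.
- Result: responder.

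**Step 3: where the gap came from.** In protocol version 1.0 these composites set every withdrawal from randomised treatment to non-responder, on the stated assumption that a severe episode would follow. The treatment-emergent wording was harmless under that rule. For the simple PPG composite, Amendment 2 strikes the rule out, keeps its equivalent for the on-treatment repeat only, and leaves the wording as it was.

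**Step 4: how many endpoints?** The simple PPG composite is clear on the page. For the other three, the markup in the text available is ambiguous:
- In both HbA1c composites the treatment-emergent clause falls inside struck-through text.
- In the triple PPG composite the old non-responder sentence appears without strike-through. If it were live, that endpoint would be protected.

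These look like markup faults, because new wording such as the reference to randomisation is struck in the same runs. They should still be checked against the PDF.

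**Step 5: size.** The amended sample size section anticipates that treatment discontinuation may be as low as 8%, with half of these leaving the trial.
- Off product but in trial: 8% × 0.5 = 4%.
- Per arm: 333 × 0.04 = 13.3. In total: 999 × 0.04 = 40.

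The documents do not say how many of these would have a severe episode after stopping, or how many would be at target. As assumptions, take 2–10% with a severe episode and 10–30% of those at target.
- Low end: 13.3 × 0.02 × 0.10 = 0.03 subjects per arm (0.01 percentage points).
- High end: 13.3 × 0.10 × 0.30 = 0.40 subjects per arm (0.12 percentage points).

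The 8% is an optimistic figure. Doubling it to 16% (also an assumption) gives 333 × 0.16 × 0.5 = 26.6 subjects, and at the high end 26.6 × 0.10 × 0.30 = 0.80 per arm, still below one.

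**The case against.** The strongest defence is that limiting hypoglycaemia to the treatment-emergent window is the plan's convention. Amended Section 17.4.2.2 compares safety endpoints on treatment, and after stopping, subjects use a marketed product chosen by the investigator, so later episodes need not be attributed to the randomised insulin. That is a coherent position for a safety endpoint. It does not govern these composites, which are efficacy endpoints placed on the in-trial period, where the glucose value is credited to the randomised arm whatever the subject is taking by then.

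A second objection is that the on-treatment repeat already gives each endpoint an analysis without the mismatch, and that nothing confirmatory depends on the in-trial version. Both statements are true. They bear on the importance of the point, not on whether the definition is consistent.

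A third is that follow-up thins out after discontinuation. Daily 4-point profiles stop, the episode record is cut to four items, and the remaining visits are mostly four-weekly instead of weekly. Counting off-product episodes therefore brings some unequal ascertainment. This stands and belongs in the fix.

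A reader might also infer that the arm with more discontinuations is favoured, and the open-label postmeal arm in particular. The documents do not support that. In the in-trial analysis a subject without a week-26 value is a non-responder, so discontinuers who leave the trial without that value count as failures, which pulls the other way. The plan gives one discontinuation rate for all arms and no ground for expecting a different rate in the postmeal arm.

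**Conclusion.** The mismatch is real. It is certain for the simple PPG composite, and probable for the triple PPG composite and the two HbA1c composites, subject to the markup check. The in-trial analysis can label as free of severe hypoglycaemia a subject whose severe episode is on record.

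Its numerical effect is very small: about 13 subjects per arm are exposed to it at the anticipated rates, and likely fewer than one per arm is misclassified. The second figure rests on the assumed ranges above. The figure of 13 should not be read as a ceiling, because the plan describes 8% as how low discontinuation might be. The direction of any between-arm bias is not known.

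Nor should the point be read as touching the trial's main conclusions. These are supportive secondary endpoints outside the five-step hierarchy, and the on-treatment repeat is unaffected. The case for acting is that the stated rule contradicts the period it is meant to serve, and correcting it is easy.

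**What to change.** For the in-trial analyses of the composite responder endpoints, define the hypoglycaemia condition as no severe episode from randomisation to week 26, on or off product, using the eDiary records kept after Visit 36A. Keep the treatment-emergent limit for the on-treatment repeat. While doing so, restate all four definitions cleanly, so that it is plain which sentences of the tracked-change text are live.

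Cost: one phrase in up to four definitions, with no new data collection, and it can be carried in the SAP before database lock. The one downside is less complete ascertainment of episodes off product. The report should say so and give the number of responders whose status changes because of an off-product episode, by arm.

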#### **Insulin dose (basal insulin dose, total and individual meal insulin dose) after 26 weeks of treatment**

Basal and bolus insulin doses will be recorded *together with date and time point (for bolus doses) of administration throughout the trial*. The insulin doses will be summarised descriptively by treatment week according to regimen, both by *time point of administration meal type* and as total daily dose in units and units/kg (total daily and separately for each mealtime dose). *Insulin doses will be summarised using the on-treatment observation period and using the SAS.*

#### **Change from baseline in lipids-lipoproteins profile after 26 weeks of treatment after randomisation (total cholesterol, high density lipoproteins, low density lipoproteins)**

*Change from baseline in lipid endpoints (LDL, HDL, and total cholesterol) will be analysed separately using a model-similar to 1). The lipid endpoints will be log-transformed before they are analysed including the corresponding baseline measurement which is included in the analysis as a covariate. The treatment difference and associated 95% confidence intervals will be back-transformed providing results in terms of ratios of geometric means on the original scale. Change from baseline in lipid endpoints (total cholesterol, HDL and LDL) after 26 weeks of treatment will be analysed based on all planned post-baseline measurements until or at 26 weeks using an MMRM similar to the model used for analysis of the primary endpoint, except with the corresponding baseline measurement as covariate.*

##### **2.29.4.2 Section 17.4.2.2 Safety endpoints**

*All safety endpoints will be compared using the on-treatment observation period. In terms of adverse events, as a minimum, serious adverse events will be tabulated separately also using the in-trial observation period.*

*All events in the in-trial observation period will be listed with information about whether it appeared in the on-treatment observation period or not.*

### **Number of treatment emergent Adverse Events AEs during 26 weeks of treatment**

AEs will be coded using the Medical Dictionary for Regulatory Activities (MedDRA). ~~All~~ AEs ~~occurring during the 26 weeks of treatment~~ will be presented based on system organ class and preferred terms.

A Treatment Emergent Adverse Event (TEAE) is defined as an event that has an onset date on or after the first day of exposure to randomised treatment, and no later than seven days after the last day of treatment.

TEAEs are summarised descriptively, whereas AE's not defined as treatment emergent are presented in listings, including AEs reported in the 30-day follow-up period. The summaries of TEAEs are made displaying the number of subjects with at least one event (N), the percentage of subjects with at least one event(%), the number of events(E) and the event rate per 100 patient years of exposure(R). These summaries are done by seriousness, severity, relation to insulin treatment, relation to device, ~~withdrawal~~ premature treatment discontinuation due to AEs and outcome.

Furthermore, summary tables based on system organ class and preferred terms are made for:

- all TEAEs
- serious TEAEs
- possibly or probably related TEAEs
- severe TEAEs
- TEAEs with preferred term that are experienced by at least 5% of the subjects in any treatment arm or by at least 5% of all subjects

For AEs where additional information is recorded, this will be summarised and listed.

AEs occurring during the run-in period are considered non treatment emergent and will be summarised separately.

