## 12 Adverse events, and technical complaints and pregnancies

### 12.1 Definitions

#### Adverse event

An AE is any untoward medical occurrence in a subject administered a product, and which does not necessarily have a causal relationship with this treatment.

An AE can therefore be any unfavourable and unintended sign (including an abnormal laboratory finding), symptom or disease temporally associated with the use of a product, whether or not considered related to the product.

An AE includes:

- A clinically significant worsening of a concomitant illness.
- A clinical laboratory adverse event (CLAE): a clinical laboratory abnormality which is clinically significant, i.e. an abnormality that suggests a disease and/or organ toxicity and is of a severity that requires active management. Active management includes active treatment or further investigations, for example change of medicine dose or more frequent follow-up due to the abnormality.

The following should **not** be reported as AEs:

- Pre-existing conditions, including those found as a result of screening procedures (pre-existing conditions should be reported as medical history or concomitant illness).
- Pre-planned procedures unless the condition for which the procedure was planned has worsened from the first trial related activity after the subject has signed the informed consent.
- Non-serious hypoglycaemia is an AE, but is reported on a hypoglycaemic episode form instead of on an AE form, see section [8.4.1.1](#).

The following three definitions are used when assessing an AE:

- **Severity**
  - **Mild** - no or transient symptoms, no interference with the subject's daily activities.
  - **Moderate** - marked symptoms, moderate interference with the subject's daily activities.
  - **Severe** - considerable interference with the subject's daily activities; unacceptable.
- **Causality**

Relationship between an AE and the relevant trial product(s):

- **Probable** - Good reason and sufficient documentation to assume a causal relationship.
- **Possible** - A causal relationship is conceivable and cannot be dismissed.
- **Unlikely** - The event is most likely related to aetiology other than the trial product.

- **Final outcome**

- **Recovered/resolved** - The subject has fully recovered, or by medical or surgical treatment the condition has returned to the level observed at the first trial-related activity after the subject signed the informed consent.

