### **12.3 Follow-up of adverse events**

The Investigator must record follow-up information by updating the forms in the eCRF.

Follow up information must be reported to Novo Nordisk according to the following:

- **SAEs:** All SAEs must be followed until the outcome of the event is “recovered/resolved”, “recovered/resolved with sequelae” or “fatal”, and until all queries have been resolved. Cases of chronic conditions, cancer or AEs ongoing at time of death (where death is due to another AE) may be closed with the outcome “recovering/resolving” or “not recovered/not resolved”. Cases can be closed with the outcome of “recovering/resolving” when the subject has completed the follow-up period and is expected by the Investigator to recover.

The SAE follow-up information should only include new (e.g. corrections or additional) information and must be reported **within 24 hours** of the Investigator's first knowledge of the information. This is also the case for previously non-serious AEs which subsequently become SAEs.

- **Non-serious AEs:** Non-serious AEs must be followed until the outcome of the event is “recovering/resolving”, “recovered/resolved” or “recovered/resolved with sequelae” or until the end of the follow-up period stated in the protocol, whichever comes first, and until all queries related to these AEs have been resolved. Cases of chronic conditions, cancer or AEs ongoing at time of death (where death is due to another AE) may be closed with the outcome “recovering/resolving” or “not recovered/not resolved”. Cases can be closed with the outcome of “recovering/resolving” when the subject has completed the follow-up period and is expected by the Investigator to recover.
- **Non-serious AE fulfilling the MESI criteria:** Non-serious AE fulfilling the MESI criteria must be followed as specified for non-serious AEs. Follow-up information on MESIs should only include new (e.g. corrections or additional) information and must be reported **within 14 calendar days** of the Investigator's first knowledge of the information. This is also the case for previously reported non-serious AEs which subsequently fulfil the MESI criteria.

The Investigator must ensure that the worst case severity and seriousness of an event is kept throughout the trial. A worsening of an unresolved AE must be reported as follow up with re-assessment of severity and/or seriousness of the event.

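### An adverse event still open from the run-in that worsens or turns serious on randomised product is not treatment emergent, so the by-arm TEAE summaries leave it out

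*Protocol*

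**What the plan says.** The current TEAE definition is in Protocol Section 17.4.2.2, as amended by Amendment 2 (2.29.4.2). A treatment emergent event "is defined as an event that has an onset date on or after the first day of exposure to randomised treatment". The definition closes the window one week after treatment ends. The same text adds that "AEs occurring during the run-in period are considered non treatment emergent and will be summarised separately". Neither rule makes an exception for a later change in the event.

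Section 12.3 governs how an open event is updated: "A worsening of an unresolved AE must be reported as follow up with re-assessment of severity and/or seriousness of the event". On non-serious events that later turn serious, its paragraph on follow-up information says: "This is also the case for previously non-serious AEs which subsequently become SAEs". It also requires that "The Investigator must ensure that the worst case severity and seriousness of an event is kept throughout the trial".

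The opening of amended Section 17.4.2.2 adds that "serious adverse events will be tabulated separately also using the in-trial observation period". Amended Section 17 starts the in-trial observation period at randomisation.

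**The concern.** Each rule is ordinary by itself; the difficulty comes from combining them. The TEAE test looks only at onset date, while the reporting rule keeps a worsening event on its first record with its first onset date. An event that started on run-in NovoRapid and became severe or serious after randomisation then has no place in the tables that compare randomised arms.

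The comparison matters here because every subject takes NovoRapid in the run-in and two of the three arms then move to faster-acting insulin aspart, whose formulation has added excipients (Section 3.3). Worsening of an open event after that switch is something by-arm safety tables should be able to show. Treatment emergent injection site reactions are a named safety endpoint, and a reaction already open at Visit 10 raises the same issue.

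**Working it through.** This is a question of definitions, and the protocol gives no figure to reproduce. The check traces one case through the rules.

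**Case.** An adverse event starts between Visit 2 and Visit 10, is unresolved at Visit 10, and becomes severe or serious on randomised product.

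1. *Is it collected?* Yes. Section 12.2 collects events from the first trial-related activity after consent.
2. *Does worsening create a new event?* Not under Section 12.3, which makes it follow-up on the existing event. The onset date stays in the run-in.
3. *Is it a TEAE?* No. Onset precedes the first day of randomised exposure, and Section 17.4.2.2 separately classes run-in events as non treatment emergent.
4. *Which tables omit it?* All TEAE summaries in Section 17.4.2.2: seriousness, severity, relation to insulin treatment, relation to device, premature discontinuation due to adverse events, outcome, and the system organ class and preferred term tables.
5. *Does the concomitant-illness rule bring it back?* Section 12.1 counts as an adverse event: "A clinically significant worsening of a concomitant illness". Section 8.2.3 limits concomitant illness to what is present at Visit 1 or found by a screening procedure. An event beginning after Visit 2 does not qualify.
6. *Do the examination sections bring it back?* In part. Section 8.4.5 asks for clinically significant worsening since screening on physical examination to be reported as an adverse event. Sections 8.4.2 and 8.4.3 ask the same for deterioration in eye findings and ECG. These cover only what those examinations detect, and they are not reconciled with the follow-up rule in Section 12.3.
7. *Does the in-trial table of serious events include it?* The protocol does not say. The in-trial period is a time window, and no rule fixes whether an event enters by onset or by the date it turned serious.

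The result is uneven. A condition present at Visit 1 that worsens after randomisation can be a new adverse event with a new onset date, and so a TEAE. A condition that began a few weeks later, in the run-in, generally cannot.

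**Illustrative size.** The protocol gives no run-in event rate. The rates and proportions below are assumptions; the 999 randomised subjects and the 8- and 26-week periods are from the protocol.

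| Step | Low | High |
|---|---|---|
| Run-in patient-years: 999 × 8 / 52.18 | 153 | 153 |
| Run-in events at 2 or 5 per patient-year (assumed) | 306 | 766 |
| Share unresolved at Visit 10 (assumed) | 15% | 30% |
| Share of those that worsen (assumed) | 3% | 10% |
| Misplaced events | 306 × 0.15 × 0.03 = 1.4 | 766 × 0.30 × 0.10 = 23 |

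At the same assumed rates, the treatment period gives 999 × 26 / 52.18 = 498 patient-years, or about 996 to 2,489 TEAEs. The misplaced events are then about 1.4/996 = 0.1% to 23/2,489 = 0.9% of TEAEs, over three arms. These count any worsening; the serious subset cannot be estimated.

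**The case against.** The best case for leaving the text alone is that little is lost. Non treatment emergent events are listed. A change to serious must be reported within 24 hours (Section 12.3), the eCRF audit trail keeps old and new values with date and time of entry (Section 13.1), and an internal committee watches safety throughout (Section 12.7.1). TEAEs are only described, never tested. Hypoglycaemia has its own onset rule and is barely touched. An event that resolves in the run-in and recurs could be a new event with its own onset, as could a distinct new diagnosis.

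All of that stands, and it rules out four stronger conclusions that a reader might draw:

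- *That the in-trial table of serious events leaves these cases out.* The text sets a window and no onset rule, so the matter is open.
- *That only concomitant illness offers a route for worsening to become an adverse event.* Sections 8.4.2, 8.4.3 and 8.4.5 give a partial one.
- *That a difference between arms could not be seen at all.* The individual events remain visible in listings and can be dated approximately from the audit trail.
- *That the run-in summary is overstated by grades reached after randomisation.* Section 12.3 does keep the worst grade on the record, but the severity and seriousness breakdowns are specified for TEAEs. No run-in table by worst grade is planned.

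None of this answers the central point: no section brings a worsening run-in event into the TEAE definition, and listings do not replace summaries by randomised arm.

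**Conclusion.** The point holds as a gap in a rule that the protocol itself fixes. An adverse event unresolved at randomisation that increases in severity or becomes serious on randomised product is excluded from the by-arm TEAE summaries. The conclusion rests on the wording of Sections 17.4.2.2 and 12.3 and on no assumed rate.

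The consequence is misplacement, with loss of the summarised comparison by arm; the data themselves are kept. The number of events is probably small, and the 1 to 23 in the illustration depends wholly on its assumptions. The change is still worth making: the excluded events can include serious ones, and the correction is cheap. It is best made while data are being collected, because without a recorded date of worsening the rule would have to be rebuilt later from audit-trail entry times.

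**What to change.** 1. In Section 17.4.2.2, extend the TEAE definition to adverse events already present at the first randomised dose that increase in severity or become serious on or after that date and within seven days after the last day of treatment. Make the sentence on run-in events subject to this.
2. In the same section, state that the in-trial table of serious adverse events includes events that become serious within the in-trial observation period, whatever their onset date.
3. In Section 12.3, require the date of worsening, or of becoming serious, on the follow-up update, so that the rule can be applied from the data.

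Re-tabulating run-in events at their Visit 10 grade is not needed. The cost is one added date item on the adverse event update, minor programming, and a slightly higher TEAE count.
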